## 8 STUDY PROCEDURES

#### 8.1 Recruitment

#### 8.1.1 Patient Identification

ACPA positive RA patients over the age of 18 will be identified by the Rheumatology outpatient department. Strategies for participant identification will be as follows:

First, to facilitate identification of RA patients already known to be ACPA+ RA, a **departmental database** of such individuals who have consented to be approached for future studies will be utilised. The Northeast Early Arthritis Cohort (NEAC) is an inception cohort of patients referred from primary care with a suspected new-onset inflammatory arthritis who consent to participate in observational research. Up to 14 individuals are enrolled every week, of whom 20% are diagnosed with RA and >250 patients with that diagnosis have already participated in this way. Importantly, the majority of these participants have given consent to be contacted to consider participation in future studies through donation of additional blood sample(s). The NEAC database captures detailed demographic, laboratory and treatment data on all cohort participants – including diagnosis and autoantibody status at inception and subsequent decision(s) regarding methotrexate treatment.

Having been identified in this way, ACPA positive RA patients will be approached during planned hospital appointments by a member of their usual care team or the rheumatology research team. Hospital appointments may be in the form of face to face visits or remote appointments by telephone, the format of the appointment will be determined by the rheumatology team in line with their standard practice. Patients will either be provided with a written information sheet at their face to face visits or by post. Alternatively, where electronically recorded evidence of current methotrexate treatment can be confirmed, information sheets may be posted to such individuals by a member of the rheumatology research team, together with contact information for the rheumatology research nurse to discuss further. If the patient is interested in participating in the study, then they can inform the rheumatology research team who will undertake a pre-screening check (see below) and, if appropriate, arrange for a screening appointment.

Second, patients with a known diagnosis of ACPA+ RA not already consented on the departmental database, will be identified during routine hospital appointments. Hospital appointments may be in the form of face to face visits or remote appointments by telephone, the format of the appointment will be determined by the rheumatology team in line with their standard practice. A member of the patients usual clinical care team will make the first approach and explain that a research study is being conducted for which they may be eligible. Patients will be provided with a written patient information sheet by the treating clinician or the rheumatology research team in person at face to face appointments or by post where remote appointments have taken place. If the patient is interested in finding out more information about the study but is not provided with a patient information sheet their clinical appointment, this will be sent out by post with a covering letter and an opt-in slip to return if the patient is interested in taking part.

#### 8.1.2 Pre-screening check

A pre-screening checklist will be completed by a member of the clinical team to determine if a patient who has contacted the department expressing interest in study participation is likely to be eligible. The pre-screening checklist could be completed during a routine appointment for patients identified in the clinic or via telephone for those who contact the department following receipt of a written information sheet. This will ensure that patients who do not meet the initial eligibility criteria are not asked to attend the hospital for any study-specific screening procedures. The following initial eligibility criteria will be confirmed:

#### Patients must be:

- Receiving methotrexate, either as monotherapy or in combination with additional conventional synthetic disease modifying drug(s) (csDMARDs) at a stable dose for at least 4 weeks prior to baseline
- If patients are receiving non-steroidal anti-inflammatory drugs (NSAID) the dose must have been stable for at least 4 weeks prior to screening.

#### Patients must not be/have;

- Using/have used another investigational medicinal products within 30 days prior to screening date
- Receiving biologic DMARD or targeted synthetic DMARD (tsDMARD)

- Receiving glucocorticoids by any route except topical/inhaled within 4 weeks of screening (nasal spray permitted).
- Serious or unstable co-morbidity deemed unsuitable by PI, eg. COPD, cardiac failure
- History of recurrent or chronic infection
- History of hepatitis B or C, syphilis, HIV, CMV or HTLV-1/2 infections (contraindication to leukapheresis)
- Known pregnancy, or women planning to become pregnant within the study period, or women who are breast feeding
- Known hypersensitivity to local or systemic corticosteroid therapy or local anaesthetic.
- Poor venous access or medical condition precluding leukapheresis

If the patient meets the initial eligibility criteria a screening visit will be arranged.

## 8.2 Screening Visit

The screening visit will take place at one of the Newcastle Hospitals (part of the Newcastle upon Tyne Hospitals NHS Foundation Trust) at least 24 hours after receipt of the study information. Participants will be provided further opportunity to discuss the study and ask any questions with a study investigator who will be a member of the clinical team. If a patient decides to participate in the study then written informed consent will be obtained prior to any study-specific screening procedures.

#### 8.3 Informed consent

Written informed consent will always be obtained prior to study specific procedures/investigations including screening blood draws. Participants in this study must have the capacity to consent for themselves. Proxy consent will not be allowed. Those wishing to take part will provide written informed consent by signing the study consent form, witnessed by the investigator with delegated responsibility (as recorded in the delegation log).

The original signed consent forms will be retained in the Investigator Site File, with copies in the hospital notes and a copy provided for the participant. The participant will specifically consent to inspection of their records by the Sponsor, Sponsor's representatives and representatives of regulatory and ethical authorities.

The right to refuse to participate without giving reasons will be respected.

Due to the small subject population, the information sheet and consent form for the study will be available only in English.

## 8.4 Study specific screening procedures

Following informed consent for the study, the participant's past medical history, full list of concomitant medication and history of blood donation will be documented in their medical records. A physical examination will be carried out consisting blood pressure, pulse, weight and height.

If any exclusions are identified at this time the patient will be deemed ineligible.

Subjects who remain potentially eligible will then go on to have the following study specific screening tests;

- Safety blood tests (FBC, U&E, LFT, ESR, clotting, electrolytes and calcium). Criteria to proceed:
  - Hb >10g/dL
  - Neutrophils >2.00x10^9/L
  - o Platelets >150x109/L
  - o eGFR >60ml/min/1.73m^2
  - o Sodium and potassium within normal laboratory reference range.
  - Normal liver function; ALT and ALP <1.5xULN. Bilirubin within the normal laboratory reference range (unless there is a reasonable explanation, at the Principal Investigators discretion, i.e. Gilbert's Disease).
- DAS 28 assessment including; swollen and tender 28-joint count, Patient Global Health Questionnaire
- Blood sample for microbiological screening (HIV, syphilis, hepatitis B and C, CMV and HTLV 1 and 2; these tests are a requirement before any of the participants' cells can enter the GMP facility)
- An electrocardiogram

A pregnancy test (urine) is required at screening for any female patients of childbearing potential (post-menopausal women must be amenorrhoeic for at least 12 months to be considered of non-childbearing potential).

Once all screening results have been reported and eligibility confirmed by an investigator the participant will be contacted to make an appointment for leukapheresis.

#### 8.4.1 Screening Failure

If the patient is deemed ineligible for study enrolment the patient will be contacted by telephone to explain this. If there is discovery of an unknown medical condition as a consequence of medical examination, ECG recording or serological screening, counselling and clinical follow up will be arranged as necessary. In such cases the patient will be contacted by telephone and either asked to come back to discuss the results with medical staff in the outpatient clinic or results will be discussed over the phone, depending on the nature and significance of the problem. A letter will be sent to the patient's GP underlining the findings and advising follow-up, with a copy sent to the patient.

## 8.5 Leukapheresis Procedure

This visit will take place no longer than 30 days after screening. Participants will visit the apheresis unit at the Freeman Hospital (part of The Newcastle upon Tyne Hospitals NHS Foundation Trust) for approximately half a day. All activities will be carried out by the clinical leukapheresis care team as per standard care for patients undergoing this procedure.

Before the procedure the Specialist Nurse/clinician will explain the procedure and answer any questions before obtaining written consent for the procedure using the standard Trust consent form for cell procurement.

On the day of the procedure and prior to the procedure a further safety blood test (FBC, U&E, magnesium and calcium) and blood pressure check are required, as per standard practice for leukapheresis.

The participant will be semi-supine on a bed and connected to the leukapheresis cell separator via a cannula in both antecubital fossa or forearm veins. The procedure takes up to three and a half hours and will only take the length of time needed to collect the sufficient number of cells required (approximately 100ml sample). When completed the needle and cannula are removed. After leukapheresis the patient will have their blood pressure checked and remain in the ward for a minimum of 10 minutes before being allowed to leave.

#### 8.6 Post intervention Assessments

A telephone follow-up consultation will take place approximately 3-4 days after leukapheresis and will be performed by a delegated member of the study team. A series of questions ascertaining to any adverse events will be asked, the answers of which will be recorded in the participants medical records.

## 8.7 Schedule of Events

The schedule of events and study activities are summarised in the table below:

Parameters	Pre-screening	Screening	Leukapheresis	Follow-up
		Vicit 1	Vicit 2	Phone call Visit 3
		Visit 1 Day 0	Visit 2 Day 15	3-4 days
		Day 0	(Day 10-30	following visit
			acceptable)	2
Pre-screening Questions	х		acceptament,	<del>-</del>
Patient Information Sheet	Х			
Screening Visit				
Written Informed Consent		х		
Medical History		Х		
Current Medication		Х		
History of blood donation		х		
Physical Examination (Cardio-				
respiratory)		Х		
Blood pressure, pulse, height and		х		
weight, venous access				
If no exclusion criteria identified pati	ent will go on the	following	<del>,</del>	<del>,</del>
Safety bloods (FBC, U&E, LFT, ESR,				
clotting, electrolytes, calcium,		Х		
magnesium)				
Screening bloods (HIV, syphilis,				
hepatitis B and C, CMV and HTLV 1		Х		
and 2) Urine Pregnancy test (for females				
of child bearing potential)		x		
ECG (12 lead)		X		
Swollen and Tender 28-Joint Count		X		
Patient Global Health VAS		^		
Questionnaire		x		
DAS28		Х		
Confirmation of eligibility		X		
Communation of engionity		^		
Leukapheresis visit				
Consent for Leukapheresis				
procedure			X	
Further safety bloods (FBC, U+E,				
magnesium, calcium)			Х	
Blood pressure prior to procedure			Х	
Leukapheresis procedure			х	
Blood pressure 10 minutes after				
procedure			Х	
Adverse Events		x	X	Х

#### 8.8 Withdrawal Criteria

Given the short duration of study participation it is not foreseen that there will be a large number of withdrawals. However, the following criteria will apply in the case of withdrawals after screening or before, during and after the leukapheresis procedure.

Participants have the right to withdraw from the study at any time without having to give a reason. The Investigator site should try to ascertain the reason for withdrawal and document this reason within the Case Report Form and participant's medical notes.

The Investigator may discontinue a participant from the study at any time if the Investigator considers it necessary for any reason including:

- Participant does not have two veins suitable for the procedure
- Significant protocol deviation or non-compliance with the study procedure
- Investigator's discretion that it is in the best interest of the participant to withdraw
- An adverse event that requires discontinuation of the leukapheresis procedure
- Termination of the study by the sponsor

Participants who are withdrawn from the study will be replaced to ensure up to six suitable samples are obtained.

## 8.9 Storage and Analysis of Samples

It is the responsibility of the study site to ensure that samples are appropriately labelled in accordance with the study procedures to comply with the Data Protection Act. Biological samples collected from participants as part of this study will be transported, stored, accessed and processed in accordance with national legislation relating to the use and storage of human tissue for research purposes and such activities shall at least meet the requirements as set out in the 2004 Human Tissue Act and 2006 Human Tissue (Scotland) Act.

The HTA consent for cell procurement will ask if the participant agrees for their cells to be stored for further research. This consent for further research will be optional.

Participant research samples will be labelled with the participant's unique study identification number only. Participant samples for toIDC manufacture will be packaged in a validated shipping container and transported by courier at ambient temperature as soon as possible after collection and on the same day as collection to the Cellular Therapies Facility at Newcastle University. The courier used for the transport of material is 1NE and should be booked using the ATOM electronic booking system. If consent for further research has not been given the samples will be destroyed at the end of the validation process.

## 8.10 End of Study

The end of the study will after the last follow up telephone call after the last participant has undergone leukapheresis.

## 9 STUDY PROCEDURE

Leukapheresis is a routine procedure used, for example, for removal of white blood cells from a donor in preparation for stem cell transplantation.

This procedure will take place at the Freeman Hospital (part of The Newcastle Upon Tyne Hospitals NHS Foundation Trust). The procedure will be carried out by the specialist nursing staff (or trained deputy), who routinely perform this procedure. Prior to the procedure routine hospital consent will be obtained by the leukapheresis team, as well as routine safety blood tests and a blood pressure check. Following the results of safety blood tests the procedure will take place.

The participant will be semi-supine on a bed and connected to the leukapheresis cell separator via a cannula in both antecubital fossa or forearm veins. The procedure takes up to three and a half hours. When completed the needle and cannula are removed and the participants are able to leave after 10 minutes, following a further blood pressure check.

## 9.1 Known Risks

There is a possibility of discovery of unknown chronic infection or medical condition as a consequence of serological screening and examination (counselling and clinical follow up will be arranged as necessary). Participants will be made aware of the tests that they will undertake prior to consent both verbally during screening and written in the patient information leaflet.

As with all blood sample collection there is a small risk of the following occurring, these are the known risks of leukapheresis;

- local anaesthetic, which may be used if required prior to cannulation, causing a 'stinging' sensation
- venepuncture and cannulation may cause pain, and lead to subsequent bruising
- arterial puncture with venepuncture and cannulation
- participants feeling faint during or after the procedure

A small amount of red cells will 'contaminate' the leukocyte product, leading to a very small risk of anaemia.

Citrate is used to prevent the blood clotting in the cell separator and citrate toxicity (a drop in blood calcium levels) may occur during the procedure, leading to tingling in the fingertips or around the mouth. Participants will be asked to report these symptoms if they occur, leading to a slowing of the leukapheresis procedure.

## **10 SAFETY REPORTING**

## 10.1 Definitions

Term	Definition				
Adverse Event (AE)	Any untoward medical occurrence in a participant, including occurrences which are not necessarily caused by or related to the intervention under study.				
Adverse Reaction (AR)	An untoward or unintended response in a participant to which is related to the intervention under study i.e. that a causal relationship between the study intervention and an AE is at least a reasonable possibility and the relationship cannot be ruled out.				
	All cases judged by either the reporting medically qualified professional or the Sponsor as having a reasonable suspected causal relationship to the study intervention qualify as adverse reactions.				
Serious Adverse Event (SAE)	
 
Results in death
 
Is life-threatening*
 
Requires inpatient hospitalisation or prolongation of existing hospitalisation
 
Results in persistent or significant disability/incapacity
 
Consists of a congenital anomaly or birth defect
 
Other important medical events that jeopardise the participant or require intervention to prevent one of the above consequences
 
				
	* - life-threatening refers to an event in which the participant was at immediate risk of death at the time of the event; it does not refer to an event which hypothetically might have caused death if it were more severe.				
Serious Adverse Reaction (SAR)	An adverse event that is both serious and, in the opinion of the reporting Investigator, believed with reasonable probability to be due to the study intervention, based upon the information provided.				
Unexpected Related Serious Event (URSE)	A serious related event, the nature and severity of which is not consistent with the known information about the intervention under study.				

## 10.2 Recording and Reporting AEs and SAEs

All AEs and SAEs occurring from the day of consent until the four day follow up telephone call is completed must be reported. Depending on the nature of the event, the reporting procedures below

will be followed. Any questions concerning adverse event reporting will be directed to the Chief Investigator or Principal Investigator in the first instance.

#### **Adverse Event (including Adverse Reaction)**

All non-serious adverse events / reactions observed at study visits, including during and after leukapheresis, will be reported on the AE study eCRF.

Severity of AEs will be graded on a three-point scale (Mild, Moderate or Severe as described in Table 10-1). Relation of the AE (i.e. causality) to the treatment will be assessed by the investigator at site.

AE Grade	Description
Mild	Discomfort is noticed but there is no disruption of normal daily activities
Moderate	Discomfort is sufficient to reduce or affect normal daily activities
Severe	Discomfort in incapacitating with inability to work or to perform normal daily
	activities

Table 10-1. AE Severity Grading

#### **Expected adverse reactions**

Adverse events and adverse reactions that occur in this study, whether they are serious or not, are expected treatment-related toxicities due to the study procedures:

- Citrate toxicity, with the most likely manifestations being tingling in the fingertips or a 'pins and needles' sensation.
- Venepuncture and cannulation may cause pain and lead to subsequent bruising.
- Anaemia

As this is a routine procedure for specialist haematology a low potential for unexpected adverse reactions exists.

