## 10.3 Recording and Reporting Unexpected Related Serious Events (URSEs)

As Leukapheresis is a routine clinical procedure to collect leukocyte samples it is not anticipated that there will URSE's. Any URSEs occurring from the intervention until 4 days post termination of the leukapheresis will be reported to the NHS REC. The NCTU, on behalf of the Sponsor, will perform this reporting.

The assessment of expectedness will be performed by the CI against the known information for the leukapheresis procedure. The reference safety information (RSI) for this study is section 9.1 - the known risks of leukapheresis. This should be used when judging expectedness.

URSEs must be reported no later than 15 calendar days after the NCTU has first knowledge of the event. Any relevant follow-up information should be sought and reported as soon as possible after the initial report.

As soon as a site suspects that a SAR may be a USRE they must contact the CI, sponsor representative and the trial manager immediately. The reporting timeframe starts at day 0 when the NCTU and/or Sponsor are in receipt of a minimum set of information:

- Sponsor study reference and study name (sponsor reference)
- Patient study number
- Date of notification of the event
- Medical description of the event
- Date and time of the onset of the event (including event end date if applicable)
- Causality assessment
- Seriousness of the event, particularly if life threatening or fatal
- An identifiable reporter (e.g., Principal Investigator)

This information must be provided by email. The site is expected to fully cooperate with the Sponsor and NCTU in order that a full and detailed report can be submitted to the NHS REC within the required timelines.

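### Section 10.2 labels three reactions expected regardless of seriousness, which leaves no room for the severity test in the URSE definition and sets up a second list beside the Section 9.1 reference; an expedited ethics report may be missed

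*Protocol*

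**What the plan says.** Under the Expected adverse reactions heading, protocol Section 10.2 says that the events it lists, "whether they are serious or not, are expected treatment-related toxicities due to the study procedures". The list has three entries: citrate toxicity, pain and bruising from venepuncture and cannulation, and anaemia. The first is worded "Citrate toxicity, with the most likely manifestations being tingling in the fingertips or a 'pins and needles' sensation".

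The definition of an unexpected related serious event (URSE) in Section 10.1 reads: "A serious related event, the nature and severity of which is not consistent with the known information about the intervention under study". Section 10.3 fixes what counts as known information: "The reference safety information (RSI) for this study is section 9.1 - the known risks of leukapheresis". It also says who decides: "The assessment of expectedness will be performed by the CI against the known information for the leukapheresis procedure".

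Section 9.1 describes citrate toxicity as a fall in blood calcium that "may occur during the procedure, leading to tingling in the fingertips or around the mouth". It names anaemia as a very small risk. It also includes items that Section 10.2 leaves out, such as "arterial puncture with venepuncture and cannulation".

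On causality, Section 10.1 accepts an adverse reaction (AR) when a link is at least reasonably possible, as judged by either the reporting medical professional or the sponsor. A serious adverse reaction (SAR) must, in the reporting investigator's opinion, be "believed with reasonable probability to be due to the study intervention".

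**The concern.** An expedited report to the ethics committee depends on three tests: the event is serious, related and unexpected. The protocol words two of these, relatedness and unexpectedness, in two ways that do not agree. In each pair, one wording can hold a report back.

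URSE reporting is the only expedited route to the ethics committee that the protocol gives for an individual adverse event. The annual progress report in Section 14.1 is another contact, but its safety content is not stated. A serious reaction wrongly classed as expected could therefore go without prompt independent review while further volunteers undergo the same procedure.

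**Working it through.** No arithmetic applies beyond a count, so the check sets the sections side by side.

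**1. The two lists.**

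| Risk | Section 9.1 | Section 10.2 |
|---|---|---|
| Citrate toxicity | yes | yes |
| Venepuncture or cannulation pain, bruising | yes | yes |
| Anaemia | yes | yes |
| Arterial puncture | yes | no |
| Feeling faint | yes | no |
| Sting from local anaesthetic | yes | no |

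Section 9.1 has 6 items and Section 10.2 has 3, all shared, so 6 − 3 = 3 appear only in Section 9.1. Section 10.2 does not refer to Section 9.1.

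**2. One event under both rules.** Take a citrate reaction that meets a seriousness criterion and goes well beyond tingling.

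- Section 10.2, read literally: it is a listed type, so it is expected whatever its seriousness. It is not a URSE and gets no expedited ethics report.
- Section 10.1 with Section 9.1 as reference: the type is known, but the severity can be judged inconsistent with the tingling described. It can then be a URSE, reportable within 15 calendar days of the trials unit's first knowledge.

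Seriousness (an outcome criterion) and severity (an intensity) are different attributes, so the two sentences are not direct opposites. They collide because a blanket expected label for serious events leaves the severity test nothing to act on.

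**3. Who applies which rule, and when.** The site comes first. Section 10.2 requires each serious event report to record whether the event is expected, and Section 10.4 asks the Principal Investigator for an opinion on expectedness. Section 10.3 requires immediate contact with the CI, sponsor representative and trial manager only once the site suspects that a SAR may be a URSE. A site working from the Section 10.2 list has no reason to suspect this for a listed reaction. The CI then assesses against Section 9.1. The conflict thus sits at the step before the CI's assessment.

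**4. Causality.** Take a serious event that the sponsor considers possibly related but the investigator does not think probably related.

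- AR: yes, because a reasonable possibility is enough and the sponsor's view counts.
- SAR: no, because the standard is probability and only the investigator's opinion counts.

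Section 10.3 starts escalation from a SAR, and Section 10.4 has the CI assign expectedness to SARs. The URSE definition itself speaks of a related event and does not require a SAR. A serious AR can therefore fall outside the procedural steps while still fitting the definition.

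**The case against.** The strongest reply is that Section 10.3 already settles the matter: Section 9.1 is the reference, the CI judges, and the Section 10.2 list is not named for URSE decisions. Serious events also go to the trials unit and the sponsor within 24 hours whatever their expectedness, so nothing is hidden. This stands in part. It limits the harm, but it does not remove a written rule that the site applies first and that says something else.

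Three stronger readings are tempting and are not supported:

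- *A serious citrate reaction or anaemia would never reach the ethics committee.* The CI's assessment against Section 9.1 can still make it a URSE.
- *The shared items are classified oppositely whenever they are serious, and the other three always.* Section 9.1 sets no explicit severity ceiling, and its remark on anaemia concerns likelihood, so a serious listed event may be expected under both sections. Section 10.2 does not claim to be exhaustive, so omission from it does not make an event unexpected.
- *Section 10.2 declares every adverse event in the study expected.* The sentence sits under its own heading and ends in a colon before a list. It is clumsy drafting.

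It is also fair that the URSE definition does not depend on the SAR definition, so the causality mismatch is not proof of suppression. The Appendix 1 safety reporting diagram could not be consulted. It may clarify the pathway, but it would not change the wording of Sections 10.1 to 10.3.

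**Conclusion.** The protocol is wrong as written, in a limited way. Section 10.2 gives an unconditional expectedness rule that cannot be squared with the nature-and-severity test in Section 10.1, and it adds a narrower list (3 of 6 items) beside the designated reference. A serious listed reaction may as a result not be escalated and may not get an expedited ethics report. Citrate toxicity is the clearest example, because Section 9.1 describes its symptoms only as tingling. The AR and SAR causality standards are a separate inconsistency that affects the same pathway.

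The conclusion assumes that a site may apply Section 10.2 literally before the CI assesses the event. The exposure is small: up to nine participants, each with one routine leukapheresis and a follow-up call 3–4 days later. Neither study outcome is affected. The documents give no event rate, so no probability can be attached.

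**What to change.** Reconcile Sections 9.1, 10.1, 10.2 and 10.3:

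- Remove the unconditional statement and the separate list from Section 10.2, and point to Section 9.1 as the single reference safety information.
- State that an event of a type listed in Section 9.1 is still assessed for unexpected severity under Section 10.1. Section 9.1 gives no severity grades, so this remains a case-by-case judgement by the CI.
- Define a SAR as an AR, on the AR causality standard and with the same assessors, that meets a seriousness criterion.
- Check that the Appendix 1 diagram agrees.

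This changes wording only. The downside is at most a rare additional expedited report.
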